#### NUMBER OF PARTICIPANTS

Following screening for inclusion into the study, approximately 50 participants will be enrolled to receive subcutaneous injections of guselkumab (100 mg). The number of dropouts in the study are expected to be low; however, additional participants will be entered to maintain the sample size and ensure that the protocol-specified number of participants complete the study.

Approximately 20 of the enrolled participants should be active nicotine users. All participants will be instructed to abstain from nicotine-containing and caffeinated products for at least 12 hours prior to the cardiology assessments.

#### INTERVENTION AND DURATION

Participants will receive guselkumab 100 mg SC injections at Weeks 0, 4, 12, 20 and 28.

The first dose of the guselkumab will always be administered at the site and by a health care professional (HCP). Subsequent doses can be self-administered at the site under supervision by site-staff after the participant has been adequately trained in the procedure.

The total duration of the study will be 40 weeks, including 28 weeks of treatment and a Final Efficacy Visit 4 weeks later (Week 32). A Final Safety Visit will occur 12 weeks after the last dose of the guselkumab (Week 40). For participants continuing to receive guselkumab commercially after the end of the study, the Final Safety Visit will occur on the same day as the first dose of guselkumab outside the study, ie, at Week 36.

#### **EFFICACY EVALUATIONS**

The following key assessments will be carried out as detailed in the Schedule of Activities. Efficacy assessments will be done locally at the sites. Results of the GLS and CFR assessments, along with other cardiology data, will be reviewed by a cardiology core lab for blinded analysis of endpoints.

- Carotid-femoral Pulse Wave Velocity
- Global Longitudinal Strain for left ventricular function
- Coronary Flow Reserve

#### SAFETY EVALUATIONS

The safety and tolerability of guselkumab will be monitored by collecting information on adverse events, clinical laboratory tests, physical examinations, vital signs, and concomitant medication review through Week 40.

#### STATISTICAL METHODS

[figure not shown]
The sample size calculation is based on the assumption that participants will show an average improvement of 20% in CFR at Week 32. To detect a CFR mean change of 0.3 from baseline with 80% power, and assuming a standard deviation of 0.8 and a 5% dropout rate, 50 participants are expected to be enrolled in the study. Sample size may be increased if the dropout rate is higher than expected, in accordance with the sample size assumptions stated above.

### **INTERIM ANALYSIS**

An interim analysis will be performed after a sufficient proportion of the participants (to be defined during the study) have accrued Week 16 CFR measurements. The scope of the interim analysis will be developed and documented in a statistical analysis plan. Other interim analyses may be planned based on specific questions from the medical field. The data from these interim analyses will allow for assessment of coverage and follow-up of participant types and treatment modalities to investigate specific research questions.

## 1.2. Schema

Figure 1: Schematic Overview of the Study

= Guselkumab 100 mg s.c.

= Cardiology Assessments (cfPWV, GLS and CFR)

= Biomarker Assessments

Visit Window between Screening Visit 1 and Screening Visit 2 = maximum of 2 weeks
Visit Window between Screening Visit 2 and Week 0 = minimum of 2 weeks and maximum of 4 weeks
CFR, GLS and cfPWV measurements at Week 0 will be considered as the baseline measurements

 $cfPWV = carotid-femoral\ pulse\ wave\ velocity;\ CFR = coronary\ flow\ reserve;\ GLS = global\ longitudinal\ strain;\ PE = Primary\ Endpoint;\ S1 = Screening\ Visit\ 1\\ (Dermatology\ Assessments);\ S2 = Screening\ Visit\ 2\\ (Cardiology\ Assessments);\ SE = Secondary\ Endpoint$ 

# 1.3. Schedule of Activities (SoA)

Phase	Screening Visit S1 (Dermatology)	Screening Visit S2 (Cardiology)	Treatment Phase						Final Final Efficacy Safety Visit a Visit b	Comments																																					
Week Visit Window (days)	Maximum of 2 weeks prior to Screening Visit S2	Minimum of 2 weeks and maximum of 4 weeks prior to Week 0			±7 -7 to ±7		20   28   ±7										-7 to ±7		32 -7 to +14	±7																											
	Screening/Administrative																																														
Informed consent form	X										Must be signed before first study-related activity.																																				
Review of inclusion/exclusion criteria	X	X	X								Refer to Section 5 to see the eligibility criteria assessed at each screening visit. Cardiology criteria to be assessed at the cardiology department at Screening Visit S2.																																				
Demography/ medical history	X	X									At Screening Visit S1, presence of PsA, psoriasis and IBD to be recorded at the Dermatology Department. At Screening Visit S2, family history and first-degree relatives with cardiovascular events to be recorded at the cardiology department.																																				
QuantiFERON-TB Gold test	X										Tests performed within 2 months before Week 0 are permitted.																																				
HBV/HCV serology	X																																														
HIV antibody test	X																																														
Chest radiograph	X										May be taken within 3 months prior Week 0.																																				
Guselkumab Admir	nistration																																														
Guselkumab SC c			X	X	X		X	X			Must be administered only on completion of all the laboratory tests, efficacy assessments, PROs and other procedures scheduled for that visit.																																				

Phase	Screening Visit S1 (Dermatology)	Screening Visit S2 (Cardiology)	Treatment Phase					Final Efficacy Visit a	Final Safety Visit b	Comments	
Week		Minimum of 2	0	4	12	16	20	28	32	40	
Visit Window (days)	Maximum of 2 weeks prior to Screening Visit S2	weeks and maximum of 4 weeks prior to Week 0		±	7	-7 to +14	±7		-7 to +14	+14 ±7	
Safety Assessments											
Physical examination (including skin)	X		X	X	X	X	X	X	X	X	Waistline circumference must be measured and documented at Screening Visit S1.
ТВ	X		X	X	X	X	X	X	X	X	Specific questions about history of TB or known occupational/personal exposure to individuals with active TB to be asked.
Vital signs	X		X	X	X	X	X	X	X	X	Blood pressure, pulse/heart rate and temperature to be recorded at the dermatology study site prior to Screening Visit S2.
Height	X										
Weight d	X		X			X			X		
12-lead ECG	X										
Pregnancy test e	X	X	X	X	X	X	X	X	X	X	
Injection-site reaction evaluation			X	X	X		X	X			
Clinical Laboratory											
Hematology, chemistry	X		X	X	X	X	X	X	X	X	Laboratory tests are described in Appendix 2.
Lipid and metabolic panel	Х					X			X		Participants must fast (ie, no food or beverages, except water) for at least 8 hours before blood is drawn. Glucose and insulin will be measured as part of this panel.
HbA1c	X					X			X		•
hsCRP	X		X			X			X		
Urinalysis	Х		X			X			Х		If there are signs of proteins and/or glucose on urine test strip, the urine sample must be analyzed centrally, protein and glucose levels must not

Phase	Screening Visit S1 (Dermatology)	Screening Visit S2 (Cardiology)		Tı		ent Pha			Final Efficacy Visit a	Final Safety Visit b	Comments
Week Visit Window (days)	Maximum of 2 weeks prior to Screening Visit S2	Minimum of 2 weeks and maximum of 4 weeks prior to Week 0	0	4 ±	7	16 -7 to +14	20 ±	7	32 -7 to +14	40 ±7	
		to week o									exceed trace levels, one re-test is allowed.
Urine nicotine test f		X	X			X			X		
Efficacy Assessmen	ts										
cfPWV g		X	X			X			X		
GLS g		X	X			X			X		
CFR g		X	X			Х			Х		Must be measured before administration of guselkumab at Week 0. Measured by Transthoracic Doppler Echocardiography with adenosine as vasodilator. CFR should be conducted regardless of a positive urine nicotine test.
PASI	X		X	X	X	X	X	X	X		
BSA	X		X	X	X	X	X	X	X		
IGA	X		X	X	X	X	X	X	X		
PSQI			X			X			X		Paper PROs completed before any other
DLQI			X			X			X		tests, procedures, evaluations, or
HADS (if available)			X			X			X		guselkumab administration on the day of the visit for Week 0 and other scheduled
AUDIT			X			X			X		visits.
Biomarkers											
Serum sample collection			X	X		X			X		Including but not limited to: hsCRP, NT-proBNP, Cytokine-levels including IL-6, IL-17A, IL-17F, IL-22, IL-23, SAA1, SAA2, Olink analysis.
Plasma sample			Х	Х		Х			Х		Concentration of oxidative lipid damage (8-Isoprostane) and malondialdehyde, concentration of antioxidants (Vitamin C and Vitamin E), adipokines (leptin and adiponectin).

Phase	Screening Visit S1 (Dermatology)	Screening Visit S2 (Cardiology)	Treatment Phase					Final Efficacy Visit a	Final Safety Visit b	Comments	
Week		Minimum of 2	0	4	12	16	20	28	32	40	
Visit Window	Maximum of 2	weeks and		±	7	-7 to	±	7	-7 to +14	±7	
(days)	weeks prior to	maximum of				+14					
	Screening Visit S2	4 weeks prior									
		to Week 0									
Urine sample			X	X		X			X		DNA damage markers (8-Oxo-7,8-dihydro2'-desoxyguanosine)
Ongoing Participant Review											
Concomitant			X (throughout the study)								
therapy											
Adverse events		·	X (throughout the study)								

Abbreviations: AUDIT= Alcohol Use Disorders Identification Test; BSA = body surface area affected by psoriasis; cfPWV = carotid-femoral pulse wave velocity; CFR= Coronary Flow Reserve; DLQI = Dermatology Life Quality Index; DNA= deoxyribonucleic acid; ECG = electrocardiogram; GLS: Global Longitudinal Strain; IL: interleukin; HADS: Hospital Anxiety and Depression Scale; HBV = hepatitis B virus; HCV = hepatitis C virus; HIV = human immunodeficiency virus; hsCRP= high-sensitivity C-reactive protein; IBD: Inflammatory bowel disease; IGA= Investigator Global Assessment; LV= left ventricular; NT-proBNP= N-terminal pro b-type natriuretic peptide; PASI = Psoriatic Area and Severity Index; PRO= Patient-reported Outcome; PsA= psoriatic arthritis; PSQI= Pittsburg Sleep Quality Index; SAA1=Serum amyloid A1; SAA2= Serum amyloid A2; SC= subcutaneous

#### Footnotes:

- a. The Final Efficacy Visit should occur 4 weeks after the last dose of the guselkumab within the study. If a participant permanently discontinues guselkumab before Week 28, the Final Efficacy Visit should take place at the time of discontinuation, or as soon as possible, and all assessments scheduled for the Final Efficacy Visit should be performed.
- b. The participant should return for a Final Safety Visit, 12 weeks after the last guselkumab dose. For participants opting to receive commercially available guselkumab after Week 28, the first dose of guselkumab outside the study (Week 36) should be considered as the Final Safety Visit.
- c. Administered at the site by health care professional (HCP) at Week 0. Subsequent doses may be self-administered at the site under supervision up to Week 28.
- d. BMI calculation is done automatically in the eCRF at each time-point when the weight is measured.
- e. Women of childbearing potential who are dosed at the clinic must have a negative serum pregnancy test at Screening Visit S1 and a negative urine pregnancy test at all other visits. Additional serum or urine pregnancy tests may be performed, as determined necessary by the investigator or required by local regulations, to establish the absence of pregnancy at any time during the participation in the study.
- f. Urine nicotine test to be done before any cardiology measurements (cfPWV, GLS and CFR). CFR should be conducted regardless of a positive urine nicotine test.
- g. At the Week 16 and Week 32 visits, participants who have been fasting for the lipid and metabolic panel are permitted to have a non-caffeinated drink prior to the cardiology assessments. Cardiology assessments (cfPWV, GLS, CFR and other assessments) must be performed at the same lab using the same machines and software, and preferably by the same cardiologist/technician at every visit. If CFR measurement is unsuccessful, ie, if the acoustic window of the coronary artery cannot be properly found, 2 attempts to measure a CFR can be made on different days. In such cases, the visit window can be extended by 7 additional days (CFR visit window=-7/+14 days). Guselkumab must not be administered at Week 0 before a CFR measurement is successfully obtained.

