## **Screening Visit S2**

Screening Visit S2 will occur no more than 2 weeks after Screening Visit S1. At the dermatology site, all participants will undergo a urine nicotine test to determine nicotine status (user/non-user) of the participant, and a urine pregnancy test (if applicable). The nicotine status (user/non-user) must be recorded in the eCRF. A positive pregnancy tests will lead to exclusion of the participant. The participants will then proceed with the cardiologic assessments performed by the cardiology investigator. A cardiologic anamnesis will be performed including cardiologic family history, vital signs and review of the relevant eligibility criteria.

Once eligibility is confirmed, the participant will undergo the cfPWV, GLS and CFR assessments. The preferred order of the cardiology assessments is cfPWV, GLS and CFR. If the participant is ineligible based on CFR results, the subsequent assessments can be deferred or avoided.

If the cardiology investigator is unsuccessful in obtaining a CFR measurement, eg, if the acoustic window of the coronary artery cannot be found, 2 additional attempts to measure the CFR can be made on different days.

## Study Visit Week 0

The Week 0 visit will occur a minimum of 2 weeks and a maximum of 4 weeks after Screening Visit S2. At this visit, the eligibility criteria will be reviewed, and the participant will complete the PRO questionnaires prior to other assessments. A physical examination including PASI, BSA, and IGA will be performed by the dermatology investigator. The PASI and IGA values will be documented but not be considered as inclusion criteria. The participants will provide serum, plasma, and urine samples, and cardiology assessments (cfPWV, GLS and CFR) will be performed by the cardiologist following a urine nicotine test to determine nicotine use by the participant, and a negative urine pregnancy test (if applicable). Only participants with CFR  $\geq$ 2 and  $\leq$ 3.5 at both Screening Visit S2 and Week 0 will be enrolled in the study. The CFR measurement at Week 0 will be considered as the baseline value. Participants will then receive the guselkumab SC injection, and may receive training for self-administration of subsequent doses in the study, if applicable.

#### Study Visits Weeks 4, 12, 20 and 28

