At these visits, participants will undergo PASI, BSA and IGA assessments as assessed by the dermatology investigator. Safety assessments including urine pregnancy test (where applicable) will be performed per the Schedule of Activities, and adverse events and concomitant therapy will be recorded. Guselkumab will be administered only after completion of all the assessments for that time-point.

#### Study Visits Weeks 16 and 32

At Week 16 and 32, the participant will complete the PRO questionnaires (DLQI first, followed by other PROs) prior to other assessments and procedures. The dermatological investigator will review the safety assessments and concomitant medication, and enquire about nicotine use in the 12 hours prior to the visit. The physical examination will include vital signs and PASI, BSA, and IGA assessments performed by the dermatology investigator. Serum, plasma, and urine samples will be drawn. After a urine nicotine test to determine nicotine use, and a negative urine pregnancy test (if applicable), the participant will proceed to the cardiology department, where the cfPWV, GLS, CFR and other assessments will be performed in arbitrary sequence by the cardiology investigator. Participants who have been fasting for the lipid and metabolic panel are permitted to have a non-caffeinated drink prior to the cardiology assessments.

If CFR measurement is unsuccessful at any time-point during the study, eg, if the acoustic window of the coronary artery cannot be properly found, 2 attempts to measure the CFR can be made on different days. At Weeks 16 and 32, the visit window can be extended by 7 additional days (CFR visit window -7/+14 days). If all 3 attempts to obtain CFR at Week 16 are unsuccessful, the participant may still proceed the study with all the scheduled procedures. Actual dates of assessments will be recorded in the source documentation and CRF.

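### Feeding state before CFR, GLS and cfPWV is not matched between Week 0 and Weeks 16 and 32, so a resulting shift could be mixed with the guselkumab effect

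*Protocol*

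**What the plan says.** **Fasting.** In the Schedule of Activities (Protocol Section 1.3) the lipid and metabolic panel is marked at S1, Week 16 and Week 32, but not at S2 or Week 0. Its comment reads: "Participants must fast (ie, no food or beverages, except water) for at least 8 hours before blood is drawn".

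**Weeks 16 and 32.** Section 8 puts the blood draw before cardiology: "Serum, plasma, and urine samples will be drawn", and after the nicotine and pregnancy tests the participant goes to the cardiology department. Footnote g and Section 8 both provide that "participants who have been fasting for the lipid and metabolic panel are permitted to have a non-caffeinated drink prior to the cardiology assessments".

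**Week 0.** Section 8 says "cardiology assessments (cfPWV, GLS and CFR) will be performed by the cardiologist following a urine nicotine test to determine nicotine use by the participant", with no mention of a fast. This is the reference visit: "The CFR measurement at Week 0 will be considered as the baseline value". Section 3 says the same for GLS and cfPWV.

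**Order.** At S2, "The preferred order of the cardiology assessments is cfPWV, GLS and CFR". Week 0 states no order. At Weeks 16 and 32, "the cfPWV, GLS, CFR and other assessments will be performed in arbitrary sequence by the cardiology investigator".

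**What is held constant.** Footnote g and Section 8.1 fix the lab, machine and software, and the operator where possible. The 12-hour caffeine and nicotine rule applies before every cardiology assessment.

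**Analysis.** SAP Section 5.3.3.1 specifies an MMRM with the baseline value, nicotine use, BMI, PsA, age, gender and visit.

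**The concern.** With no control arm, the effect estimate is the mean change from Week 0. A measuring condition that tends to differ between Week 0 and the later visits feeds straight into that mean, and a larger sample does not remove it. The primary endpoint and the GLS and cfPWV secondary endpoints, at both time points, are all exposed.

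The protocol's own text gives reason to take physiological state seriously. Section 2 stresses accurate measurement of both basal and maximal coronary flow, and describes a microvascular endothelium that reacts quickly to hormones and metabolites. Table 1 in Section 6.5.3 lists insulin, as a drug, among the agents that raise CFR. None of this says that a meal changes CFR. It does show that the protocol treats conditions at the time of scanning as relevant.

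**Working it through.** **1. The visits side by side**

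| Visit | Fasting panel | Expressly allowed between draw and cardiology | Order of assessments |
|---|---|---|---|
| S2 (eligibility) | No | Not applicable | Preferred: cfPWV, GLS, CFR |
| Week 0 (baseline) | No | Not applicable | Not stated |
| Week 16 | Yes, 8 h | Non-caffeinated drink | Arbitrary |
| Week 32 (primary) | Yes, 8 h | Non-caffeinated drink | Arbitrary |

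**2. Is there a fasting rule at Week 0 elsewhere?** The only candidate is Section 5.3, item 4. Its 12-hour caffeine rule includes the word *food* in a list of caffeinated items. Read as caffeinated food, it says nothing about meals. Read as all food, it would impose the same fast at every cardiology visit. The first reading is more natural. The item opens with caffeine's antagonism of adenosine, and the other statements of the 12-hour rule (Section 4.1, inclusion criterion 20, exclusion criterion 5) name only caffeine and nicotine. Footnote g also treats fasting as something that comes from the panel at Weeks 16 and 32. The wording is still ambiguous.

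**3. Would the analysis detect or remove a shift?** The model has no fasting term. Its visit term separates Week 16 from Week 32, but both are fasting-draw visits. The S2 versus Week 0 comparison in SAP Section 5.7.7 uses two visits without the panel. A shift common to both nicotine groups would cancel in the user versus non-user contrast. It would not cancel in the overall change, which is what the hypothesis in SAP Section 2 concerns.

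**4. Illustrative size**

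The plan's own figure first. Protocol Section 9.2 gives a change of 0.3, SD 0.8, 80% power, 5% dropout and 50 participants. For a one-sample test, n = (SD × (z_alpha + z_power) / change)².

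- Two-sided 0.05: (0.8 × 2.80 / 0.3)² = 55.8, so 56 (58 by the t-test). Dividing by 0.95 gives 59 (62).
- One-sided 0.05: 44 (46 by the t-test). Dividing by 0.95 gives 47 (49).

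So 50 is not reproduced at the stated two-sided level; the one-sided t-test comes close, at 49. That is a separate matter and is noted only because these inputs are reused.

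Assumptions: 47 completers (50 × 0.95 = 47.5, rounded down), SD of change 0.8, two-sided 0.05 one-sample t-test, and a constant shift b due to measuring conditions alone.

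| Size of b | Share of 0.3 | Shift +b, no drug effect: chance of a significant increase | Shift −b, true effect 0.3: power |
|---|---|---|---|
| 0 | 0% | 2.5% | 71.1% |
| 0.05 | 17% | 6.2% | 55.5% |
| 0.10 | 33% | 13.1% | 38.9% |
| 0.15 | 50% | 24.2% | 24.2% |

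For scale, take CFR as hyperaemic over resting velocity, starting at 2.75, the midpoint of the 2 to 3.5 eligibility range. If only resting velocity changed, a 5% fall gives 2.75 / 0.95 = 2.895 (+0.145), and a 5% rise gives 2.75 / 1.05 = 2.619 (−0.131). The 5% is also an assumption.

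**The case against.** The strongest objections, and what stands of each:

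- **The fast belongs to the draw, not the scan.** This stands. Food after the draw is not expressly barred, the interval to cardiology is not stated, the permitted drink may contain calories, and repeat CFR attempts may fall on other days. A reader might infer that every follow-up scan is made after an 8-hour fast; the text does not go that far.
- **Fed baselines are not shown.** This also stands. With no rule, participants may arrive at Week 0 fed or fasted. A reader might infer a uniform fed-to-fasted shift in every change score; the documents establish only that the condition is unmatched.
- **The word *food* in Section 5.3 may already require a fast everywhere.** This is possible but the weaker reading. It calls for clarification and does not dispose of the point.
- **The core lab's echocardiology protocol may set preparation and order.** It governs GLS and CFR and is not among the documents, so this cannot be excluded for those two measures. It is not cited for cfPWV, and Section 8 itself leaves the order at Weeks 16 and 32 open.
- **Order does not change from baseline.** This is correct. The preferred order belongs to S2, which is screening, and Week 0 states none. A reader might infer that order becomes arbitrary only after baseline; the text does not show that. Section 2.3.1 gives adenosine a half-life under 10 seconds, so carry-over into GLS or cfPWV is likely to be small.
- **The study has stopped.** SAP Section 1 records termination on 31 May 2023, so schedule changes can only help a successor study.

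**Conclusion.** The point holds as a failure to standardise. Follow-up cardiology is scheduled after a fasting draw, baseline is not, and neither the design nor the model can separate a resulting shift from a guselkumab effect.

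Direction and size are unknown. The table in the working shows only that a shift well below the 0.3 target would matter in either direction at the planned sample size. With the smaller number actually enrolled, a given shift would produce a false significant result less often, but the bias in the estimated mean change would be the same. A reader might push the velocity arithmetic to a 10% fall in resting velocity and conclude that fasting could account for the whole target effect (2.75 / 0.90 = 3.056, or +0.306). The documents do not support that: they give no effect of feeding on CFR, GLS or cfPWV, and a 10% rise would move CFR the other way (2.75 / 1.10 = 2.50, or −0.25).

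The conclusion assumes that *food* in Section 5.3 means caffeinated food and that the core lab protocol does not already impose the same preparation at every visit. The order issue is minor and concerns mainly GLS and cfPWV.

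**What to change.** **For the design, or a successor study**

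1. Apply one pre-cardiology fasting and drink rule at S2, Week 0, Week 16 and Week 32, tied to the cardiology assessment and covering repeat CFR attempts. At Week 0 the simplest route is to add the lipid and metabolic panel to the existing draw. S2 has no draw and needs its own instruction.
2. Reword Section 5.3, item 4, so that *food* clearly means either caffeinated food or all food.
3. Use the order cfPWV, GLS, CFR at every cardiology visit, in place of the arbitrary sequence at Weeks 16 and 32.

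Adding the panel at Week 0 has a second benefit. SAP Section 5.6.3.1 names Week 0 as the laboratory baseline and lists this panel, yet the Schedule of Activities has no Week 0 sample for it.

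**For the data already collected**

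State in the SAP and the report that change from Week 0 in CFR, GLS and cfPWV cannot be separated from a possible change in feeding state, and do not attribute it to guselkumab alone.

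**Cost.** Participants fast before two more visits, and one panel is added to a draw already taken. The rest is edits to the schedule and visit text, with no added visits. The reporting statement costs a few sentences.
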